#### 4.2.4 Prior medication for Cushing's disease

Prior medication for Cushing's disease will be summarized by preferred term, overall and by cohort. This summary will be prepared for the FAS and the subgroup of patients from German sites.

#### 4.2.5 Prior and concomitant therapy

Prior and concomitant medications and significant non-drug therapies will be listed and summarized by cohort in the safety set.

Medications will be classified as prior or concomitant based on the following rules and will be coded using the WHO Drug Reference List (WHO DRL) dictionary that employs the WHO Anatomical Therapeutic Chemical (WHO ATC) classification system:

- Prior medications are medications that started before the first dose of study drug regardless of whether the medication ended before or after the first dose of study drug.
- Concomitant medications are medications that started on or after the first dose of study drug, or started before the first dose of study drug, and continued after the first dose of study drug.

The number and percentage of patients with prior and concomitant medications will be presented separately by ATC class and preferred term according to the WHO DRL dictionary.

---

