3.1.1 Safety and tolerability assessments

All safety assessments will be collected from patient's enrollment into the study by signing the informed consent or acknowledging an equivalent document (e.g., written information) as per country regulation until the last dose of pasireotide s.c. at the patient's last follow-up visit within the 3 year observation period or until 3 months after the last dose for patients who permanently discontinue pasireotide s.c. prior to completing 3-year observation period.

- Adverse events and Serious Adverse Events will be followed-up and collected from patient's enrollment into the study until 28 days after the last dose of pasireotide s.c. at the patient's last follow-up visit. Adverse events and Serious Adverse Events will be collected until 3 months after the last dose for patients who permanently discontinue pasireotide s.c. prior to completing 3-year observation period.
- Special safety assessments will be collected from patient's enrollment into the study until the last follow-up visit as available or until 3 months after the last dose for all available safety parameters, for patients who permanently discontinue pasireotide s.c. prior to completing the 3-year observation period. Safety data to be collected include: vital signs, blood pressure, heart rate, body temperature, blood glucose (fasting plasma glucose, HemoglobinA1c), hormones (IGF-1, GH, TSH/free T₄), liver enzymes (AST, ALT, alkaline phosphatase, γGT, total bilirubin), hematology, electrolytes, immunological events (e.g., allergic reactions: rash, pruritus, injection site reactions), gallbladder ultrasound and ECGs.
- Medical history including history of smoking, history of alcohol use, presence of hepatitis B and C infection will be recorded at patient's entry in the study. Prior/concomitant medications/significant non-drug therapies (e.g., surgery, radiation) will be collected from patient's enrollment into this study until the last follow-up visit as available or until 3 months after the last dose for patients who permanently discontinue pasireotide s.c. prior to completing the 3-year observation period.

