6.3 Treatments (pasireotide s.c., concomitant therapies)

The medication for this study is pasireotide s.c. Prescribing information on the pasireotide s.c. start and stop dates, dose, dose changes and reason for changes. The actual mean daily dose and duration of drug exposure while in the study will be summarized by descriptive statistics and corresponding listing will be presented. Incidence rates by person-time of exposure and incidence rates by person-time of observation with their corresponding 95% confidence interval will be reported.

Concomitant medications and significant non-drug therapies prior to and after enrolling into the study will be summarized by preferred term and ATC class of the WHO-Drug Reference List.

These analyses will be performed on the safety set.

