## 5.2 *Concomitant medication date imputation*

Partial concomitant medication start dates are imputed with reference to the treatment start date as outlined below.

Completely missing start dates will not be imputed.

Any missing date will be queried for resolution. For any unsolved missing dates, the following rules in the following order will be applied to decide if a concomitant medication or a significant non-drug therapy was taken after the start of the study treatment and to decide if the data should be included in the summary table. Originally collected date will be listed in listings.

CM start date imputation:

1. If the CM start date year value is missing, the imputed CM start date is set to one day prior to treatment start date.
2. If the CM start date year value is less than the treatment start date year value, the CM started before treatment. Therefore:
  - a. If the CM month is missing, the imputed CM start date is set to the mid-year point (01JulYYYY).
  - b. Else if the CM month is not missing, the imputed CM start date is set to the mid-month point (15MONYYYY).
3. If the CM start date year value is greater than the treatment start date year value, the CM started after treatment. Therefore:
  - a. If the CM month is missing, the imputed CM start date is set to the year start point (01JanYYYY).
  - b. Else if the CM month is not missing, the imputed CM start date is set to the month start point (01MONYYYY).
4. If the CM start date year value is equal to the treatment start date year value:
  - a. And the CM month is missing or the CM month is equal to the treatment start date month, then the imputed CM start date is set to one day prior treatment start date.
  - b. Else if the CM month is less than the treatment start date month, the imputed CM start date is set to the mid-month point (15MONYYYY).
  - c. Else if the CM month is greater than the treatment start date month, the imputed CM start date is set to the month start point (01MONYYYY).

CM end date imputation:

1. If CM end day is missing and CM month/year are non-missing then impute CM day as the minimum of treatment end date and the last day of the month.
2. If CM end day/month are missing and CM year is non-missing then impute CM day as the minimum of treatment end date and the end of the year (31DECYYYY).
3. If CM day/month/year is missing then use the treatment end date + 1 day as the imputed CM end date.

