4. If imputed CM end date is less than the CM start date, use the CM start date as the imputed CM end date.

---

- If complete (imputed) CM end date is available and the imputed CM start date is greater than the (imputed) CM end date, then imputed CM start date should be set to the (imputed) CM end date.

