#### 8.2.1 Secondary efficacy endpoints

The secondary efficacy endpoints are as follows:

---

1. Proportion of patients with a mean UFC  $\leq$  ULN at 1, 3, 6, 12, 24 and 36 months after enrollment into the study.
2. The absolute and percentage change from baseline in biochemical measures of disease activity (mean UFC, serum cortisol, serum cortisol after dexamethasone, salivary cortisol, ACTH, fasting serum lipid profile (total cholesterol, HDL, LDL)) over time.
3. Proportion of patients achieving normalization of biochemical measures of disease activity (serum cortisol, serum cortisol after dexamethasone, salivary cortisol, ACTH) over time, where normalization refers to being within the upper and lower limit of normal ranges.
4. The absolute and percentage change from baseline in clinical signs and symptoms (blood pressure, body weight, body mass index, waist circumference) over time.
5. The proportion of patients with favorable shift from baseline in clinical symptoms of Cushing's disease over time.
6. The change from the last dose of pasireotide s.c. to 90 days after permanent discontinuation of pasireotide s.c. for patients who discontinue pasireotide s.c. prior to completing 3-year observation period. This change will be evaluated for all available continuous efficacy parameters.
7. The absolute and percentage change from baseline in tumor size over time.
8. The absolute and percentage change from baseline in patient reported outcome questionnaires (Cushing QoL and EURO QoL) over time.

All efficacy analyses will be done for all patients in the FAS and for the two cohorts. And all efficacy analyses except those under 5 will be done for the subgroup patients from German sites. Additionally, the efficacy analyses described under 1, 2, and 3 above will be repeated for the following subgroups of patients:

- Patients treated with monotherapy pasireotide s.c. throughout the study
- Patients treated with a combination of pasireotide s.c. with any other therapy for Cushing's disease throughout the study
- Patients who switched from monotherapy to combination therapy or vice versa at any time during the study

For all continuous efficacy variables (biochemical measures of disease activity, blood pressure, body weight, body mass index, waist circumference, tumor size), a Mixed Effects Repeated Measures Model will also be employed to assess the longitudinal changes in these variables.

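### SAP 4.2.5 defines concomitant medication by the first dose only, so medications begun after pasireotide s.c. was stopped are counted as concomitant

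*SAP*

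**What the plan says.** SAP 4.2.5 has two routes into the concomitant category. The first is by start date: "Concomitant medications are medications that started on or after the first dose of study drug". The second covers medications that "or started before the first dose of study drug, and continued after the first dose of study drug". Both refer to the first dose only. The numbers and percentages of patients are then tabulated by ATC class and preferred term in the safety set.

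Protocol 3.1.1 sets how long medications and significant non-drug therapies such as surgery and radiation are collected: "until the last follow-up visit as available or until 3 months after the last dose for patients who permanently discontinue".

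SAP 5.2, which handles incomplete dates, has a purpose tied to the same single reference point. Its rules serve "to decide if a concomitant medication or a significant non-drug therapy was taken after the start of the study treatment", and so determine what enters the summary table.

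Protocol 6.3 is no narrower: "Concomitant medications and significant non-drug therapies prior to and after enrolling into the study will be summarized by preferred term and ATC class". It splits at enrolment and sets no end at the last dose.

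**The concern.** For patients who stop early, the database will hold therapies that began after the last pasireotide dose. Replacement treatment for Cushing's disease is foreseeable in that window, since Protocol 3.4.1.1 lists unsatisfactory therapeutic effect among the withdrawal reasons. Under SAP 4.2.5 a replacement drug begun after stopping receives the same label as a drug given alongside pasireotide, and the table cannot tell the two apart.

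The SAP draws this line for other data. Efficacy analyses use values up to 3 days after the end of treatment, apart from the planned comparison with 90 days after stopping. Safety analyses treat the first 28 days after the last dose as on-treatment, and post-treatment adverse events have their own summary (8.4.1). No post-treatment category exists for medications.

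What is at stake is an accurate description of what was taken together with pasireotide. There is a possible further effect on the 8.2.1 efficacy subgroups, one of which is defined as "Patients who switched from monotherapy to combination therapy or vice versa at any time during the study".

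**Working it through.** The plan states no figure on this point, so there is nothing to reproduce. The check applies the written rules to test dates.

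**Rule.** Let S and E be the start and end of a medication, F the first dose and L the last dose.

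- SAP 4.2.5: concomitant if S ≥ F, or if S < F and the medication continued after F. L does not appear.
- Comparison rule: the same, and also S ≤ L.

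**Test patient.** F = 10 Jan 2017, L = 10 Mar 2018 (dates chosen for illustration).

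| Medication | SAP 4.2.5 | With S ≤ L added |
|---|---|---|
| 1 Jun 2017 to 1 Jan 2018 | concomitant | concomitant |
| 1 Jun 2016 to 1 Jun 2017 | prior and concomitant | prior and concomitant |
| 1 Jan 2016 to 1 Jun 2016 | prior only | prior only |
| starts 11 Mar 2018 (L + 1 day) | concomitant | not concomitant |
| starts 9 May 2018 (L + 60 days) | concomitant | not concomitant |

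The two rules differ only for medications begun after the last dose.

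**Do the date rules of SAP 5.2 remove such records?** They do not.

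- Start recorded as Apr 2018, end as May 2018. The start is imputed as 1 Apr 2018. The end is the earlier of L and 31 May 2018, which is 10 Mar 2018. That precedes the start, and SAP 5.2 then says: "If imputed CM end date is less than the CM start date, use the CM start date as the imputed CM end date". The end becomes 1 Apr 2018.
- Start 20 Apr 2018, end fully missing. The end is set to L + 1 day = 11 Mar 2018, then reset to 20 Apr 2018 by the same rule.

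Both records stay in the table with a start after L.

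**How far does it reach?**

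- *Concomitant table (4.2.5):* affected, for early discontinuers, for starts in roughly the 3 months after the last dose.
- *Single/combination/switch table (8.3):* not affected. It has its own definitions, and each period includes only patients still receiving pasireotide at the end of that period.
- *Therapy subgroups (8.2.1):* unsettled. They are worded over the whole study with no end at the last dose. On one reading, a patient on monotherapy up to the last dose who starts another drug during follow-up leaves the monotherapy subgroup, although the efficacy values analysed are on-treatment apart from the comparison after discontinuation.
- *Primary endpoint (8.4.1):* not affected. It counts patients with adverse events that the investigator suspects are related to pasireotide, and does not use the medication label.

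**The case against.** The strongest reply is that this is one descriptive table whose rule is explicit, so it shows what it defines. Protocol 6.3 is equally open-ended, so the SAP does not depart from the protocol. No objective or endpoint asks for subsequent therapy. Therapies are also listed, with dates as collected, so a reader could compare start dates with the last dose. All of this stands and limits the importance of the point. It does not make the label right: a percentage headed concomitant should not count drugs begun after the study drug ended, and listings do not correct a summary percentage.

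A reader might infer that the plan overstates combination use in general. The documents do not support that. Combination use is reported in 8.3, where therapy begun after stopping cannot enter. Nor do they show that the 8.2.1 subgroups are wrong. Those subgroups speak of pasireotide combined with another therapy, which on an ordinary reading excludes a drug begun after pasireotide ended, and nothing says that they use the 4.2.5 classification. What remains there is loose wording.

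The rules and the ATC/preferred-term sentence in SAP 4.2.5 name medications only. Non-drug therapies are listed and summarised, but only Protocol 6.3 places them under ATC class and preferred term.

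A cut exactly at the last dose has a cost too. A drug started on day 10 after the last dose to treat a treatment-emergent adverse event would be labelled post-treatment, while the event itself falls in the 28-day on-treatment period. This objection is sound and is met in the fix.

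**Conclusion.** The point holds for the concomitant-medication summary. As written, SAP 4.2.5 counts medications begun after pasireotide was stopped as concomitant, Protocol 3.1.1 ensures that such records are collected where available, and SAP 5.2 keeps them. The impact is limited to this supportive table and possibly the 8.2.1 subgroups.

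No size should be claimed. A reader might multiply a guessed early-discontinuation rate by a guessed rate of starting replacement therapy and read the product as the share of patients wrongly shown on a concomitant Cushing's therapy. The documents give neither rate. The product would also overstate the error at patient level, because a patient who already took another Cushing's therapy alongside pasireotide is correctly counted as having had one. It would further ignore incomplete data after stopping. The conclusion rests only on the wording of the rules and on at least some patients starting a medication in the follow-up window.

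**What to change.** In SAP 4.2.5, define concomitant as use overlapping the interval from the first on-study dose to the treatment end date, both already derived in 6.1.2. Flag medications and non-drug therapies that start after that date as post-treatment, and tabulate them separately for patients who discontinued early. Base the flag on the start date, because SAP 5.2 imputes missing end dates from the treatment end date.

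In the post-treatment table, identify starts within 28 days of the last dose, so that it can be read against the treatment-emergent adverse event tables.

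In SAP 8.2.1, state that the monotherapy, combination and switch subgroups are assigned only from therapies used up to the last pasireotide dose, to match the on-treatment efficacy values.

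SAP 8.3 needs no change.

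The cost is a few sentences, one derived flag and one extra table from data already collected. The reported concomitant-use percentages will be somewhat lower.

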## 5 HANDLING OF MISSING DATA AND OUTLIERS

### 5.1 AE date imputation

Partial adverse event start dates are imputed with reference to the treatment start date. Completely missing start dates will not be imputed.

Any missing onset date, causality, or severity must be queried for resolution. Unsolved missing values will be imputed according to the following:

AE start date imputation:

1. If the AE start date year value is missing, the date uncertainty is too high to impute a rational date. Therefore, if the AE year value is missing, the imputed AE start date is set to NULL.
2. If the AE start date year value is less than the treatment start date year value, the AE started before treatment. Therefore:
  - a. If AE month is missing, the imputed AE start date is set to the mid-year point (01JulYYYY).
  - b. Else if AE month is not missing, the imputed AE start date is set to the mid-month point (15MONYYYY).
3. If the AE start date year value is greater than the treatment start date year value, the AE started after treatment. Therefore:
  - a. If the AE month is missing, the imputed AE start date is set to the year start point (01JanYYYY).
  - b. Else if the AE month is not missing, the imputed AE start date is set to the later of (month start point (01MONYYYY), AE start reference date + 1 day).
4. If the AE start date year value is equal to the treatment start date year value:
  - a. And the AE month is missing the imputed AE start date is set to the AE reference start date + 1 day.
  - b. Else if the AE month is less than the treatment start month, the imputed AE start date is set to the mid-month point (15MONYYYY).
  - c. Else if the AE month is equal to the treatment start date month or greater than the treatment start date month, the imputed AE start date is set to the later of (month start point (01MONYYYY), AE start reference date + 1 day).

AE end date imputation:

1. If the AE end date month is missing, the imputed end date should be set to the earliest of the (treatment follow up period date, 31DECYYYY, date of death).
2. If the AE end date day is missing, the imputed end date should be set to the earliest of the (treatment follow up period date, last day of the month, date of death).
3. If AE year is missing or AE is ongoing, the end date will not be imputed.

If complete (imputed) AE end date is available and the imputed AE start date is greater than the (imputed) AE end date, then imputed AE start date should be set to the (imputed) AE end date.

---

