#### 6.1.2 Study drug start and end date

Treatment start date for cohort 1: defined as the first date at which a non-zero dose of pasireotide s.c. was administered during the study and recorded on the DAR (e)CRF.

Treatment start date for cohort 2: defined as the first date at which a non-zero dose of pasireotide s.c. was administered prior to study entry and recorded on the CMD (e)CRF.

Treatment end date (same for the 2 cohorts) (The date of last administration of study drug) is defined as the last date at which a non-zero dose of study drug was administered and recorded on the DAR (e)CRF. If the end of the last dosing period with a non-zero dose is missing, the "last known date patient took study drug" (as reported on the completion panel (CMP)) will be used.

Date of first dose after informed consent (IFC): defined as the first date at which a non-zero dose of pasireotide s.c. was administered during the study (i.e. after IFC) and recorded on the DAR (e)CRF.

If treatment with pasireotide s.c. is still ongoing at the time of data cut-off for analysis (i.e. no end date on DAR and CMP (e)CRF), it will be assumed that treatment was ongoing until the last contact date (see Section 6.1.4).

Periods with a specific dose of study medication may have incomplete start and/or end dates (e.g. FEB2015 to MAR2015), however, it is assumed that month and year are always known. If the day is missing in the start date,

- the 15th of the respective month is used for imputation, if not before the end date of the previous period,
- the day after the previous end date is used otherwise.

After imputation of start dates, incomplete end dates are imputed. The unknown end date is set

- to one day before the next start date if the known month and year are equal to month and year of the next start - 1 day
- to the last day of the known month otherwise.

---

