### 6.1.5 Study day

Study days are calculated relative to the date of first dose during the study. The date of first dose defines Day 1. Day -1 is one day before Day 1, Day -2 two days before Day 1, Day 2 one day after Day 1, and so on. That is, there is no Day 0.

More specifically, the study day is calculated as

study day = (date of assessment/event - date of first dose) + 1

if the assessment or event is on or after the date of first dose, and as

study day = (date of assessment/event - date of first dose)

otherwise.

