#### 6.2.4 Confidence intervals for occurrence rates of AEs and SAEs

The occurrences of AE or SAE by preferred term will be modeled to follow approximately a Poisson process with constant intensity  $\theta$ . The rate parameter  $\theta$  will be estimated as  $\lambda=D/T$ , where

- Numerator ( $D_i$ ) = total number of events (AE or SAEs by PT) observed within the cohorts and overall ( $i=1,2,3$  for cohort 1, 2 and overall, respectively). PTs which were reported more than once on the same day (within the same patient) will be counted as one event under the highest severity grade.
- Denominator ( $T_i$ ) = The sum of exposure time  $t$  across all patients in group  $i$  per 100 patient years. For a single patient the exposure time  $t$  is derived as:  $t = (\text{minimum date of (last dose + 28 days, last contact day, analysis cutoff day)} - \text{date of first dose during study} + 1) / 365.25$ . The sum of the exposure time of all patients in group  $i$  will be divided by 100 to obtain the exposure time per 100 patient years.
- Note: the analyses of safety and tolerability assessments will concentrate on the on-treatment period, defined to be the period from Day 1 to 28 days after last dose of pasireotide s.c. i.e. the exposure period for  $T_i$  is accordingly adjusted.

Conditionally on  $T$ , an exact  $100*(1-\alpha)\%$  confidence interval for a Poisson variable with parameter  $\theta*T$  and observed value  $D$  can be obtained based on (Garwood, 1936), from which an exact  $100*(1-\alpha)\%$  confidence interval for  $D/T$  will be derived as follows (Sahai, 1993; Ulm, 1990):

$$\text{Lower confidence limit } L = \frac{0.5c_{\alpha/2,2D}}{T} \quad (\text{in SAS: } (0.5*\text{cinv}(\alpha/2,2*D(i))/T(i))$$

$$\text{Upper confidence limit } U = \frac{0.5c_{1-\alpha/2,2D+2}}{T} \quad (\text{in SAS: } (0.5*\text{cinv}(1-\alpha/2, 2*D(i)+2)/T(i)) \text{ for } i=1,2,3 \text{ and } D(i) > 0 \text{ and } 0 \text{ otherwise,}$$

where  $c_{\alpha,k}$  is the  $\alpha$ th quantile of the Chi-square distribution with  $k$  degrees of freedom.

Garwood, F. 1936. Fiducial limits for the Poisson distribution. *Biometrika*. 28(3/4):437-442

Ulm, K. 1990. A simple method to calculate the confidence interval of a standardized mortality ratio. *American Journal of Epidemiology* 131(2):373-375.

Sahai, H. and Khurshid, A. (1993a). "Confidence intervals for the mean of a Poisson distribution: A review", *BiomtrcJ*, 35, 857-867.

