## 8.4 SAFETY ANALYSIS

Safety and tolerability assessments include AEs, vital signs (blood pressure, heart rate, body temperature), blood glucose (fasting plasma glucose, Hemoglobin A1c), hormones (GH, IGF-1, TSH/free T4), liver enzymes (AST, ALT, alkaline phosphatase,  $\gamma$ GT, total bilirubin), hematology, electrolytes, gallbladder ultrasound and ECGs.

The analyses of safety and tolerability assessments will concentrate on the on-treatment period, defined to be the period from Day 1 to 28 days after last dose of pasireotide s.c. Post-treatment events and assessments (i.e. events and assessments started or performed after the on-treatment period) will be analyzed. In particular, the change between on-treatment period and the period from 28 days after last dose of pasireotide to 90 days after discontinuing pasireotide s.c. treatment will be investigated for continuous parameters in patients who permanently discontinue pasireotide s.c. prior to completing the 3-year observation period.

All safety analyses will be based on the safety set and summarized overall and by cohort. Baseline is described in Section 6.1.6

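### For patients already on pasireotide at entry, partial AE dates are imputed from a pre-study date, so some on-study AEs fall before Day 1; dose intensity also mixes pre-study and on-study time

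*SAP*

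**What the plan says.** SAP 5.1 (AE date imputation): "Partial adverse event start dates are imputed with reference to the treatment start date". The rules then branch on how the AE year and month compare with that date:

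- Rule 3a (AE year later than treatment start year): "If the AE month is missing, the imputed AE start date is set to the year start point (01JanYYYY"). No lower bound applies.
- Rules 3b and 4c use "the later of (month start point (01MONYYYY), AE start reference date + 1 day").
- Rule 4a (same year, month missing): "the imputed AE start date is set to the AE reference start date + 1 day".

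The two reference-date terms in rules 3b, 4a and 4c are worded differently, and neither is defined.

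SAP 6.1.2 gives the treatment start date by cohort. For Cohort 2 it is "defined as the first date at which a non-zero dose of pasireotide s.c. was administered prior to study entry". SAP 8.3 repeats this.

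The analyses that use the imputed date start elsewhere. SAP 6.1.5: "Study days are calculated relative to the date of first dose during the study". The person-time formula in SAP 6.2.4 subtracts the "date of first dose during study". SAP 8.4 has the on-treatment period "defined to be the period from Day 1 to 28 days after last dose of pasireotide s.c". SAP 8.4.1 counts an AE as treatment-emergent if it began or worsened in that period.

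On exposure, SAP 8.3 divides total cumulative dose by the duration of exposure, which runs from the cohort-specific treatment start. It then labels the result as dose intensity during the study, which is also what Protocol 6.3 asks for. The same section defines a duration of on-study exposure, but the dose-intensity formula does not use it.

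**The concern.** In Cohort 2 the imputation is anchored months or years before the period in which AEs are counted. A date imputed as being after treatment start can therefore still fall before Day 1. Protocol 3.5.2.1 collects AEs only after consent, so for an event that began on study such a date is wrong.

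The error can only remove on-study events, and only from Cohort 2. In the exposure-adjusted rates the event leaves the numerator while the patient's time stays in the denominator. SAP 8.4.1 offers those rates as the aid to interpreting differences between cohorts. The primary endpoint (patients with related AEs and SAEs) is exposed as well, but it counts patients, so it changes only when the misdated event is the patient's sole qualifying one.

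The dose-intensity figure for Cohort 2 would not describe the same quantity as the figure for Cohort 1.

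**Working it through.** The documents give no figure of their own on this point. The check applies the SAP 5.1 rules and the SAP 6.1.5 study-day formula to illustrative dates.

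**Assumed Cohort 2 patient.** Pasireotide started 10 Mar 2014; first on-study dose (Day 1) 20 Sep 2015. For dates before Day 1, study day = date − first dose; otherwise add 1.

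1. AE recorded as `2015`. The AE year is later than 2014, so rule 3a gives 01JAN2015. 01JAN2015 − 20SEP2015 = −262, i.e. Day −262. Rule 3a does not use the undefined reference date, so this result does not depend on how that term is read.
2. The same record in a Cohort 1 patient with first dose 20SEP2015. The years are equal, so rule 4a applies. Taking the reference date as treatment start, the result is 21SEP2015 = Day 2, and the AE counts.
3. AE recorded as `SEP2015`, Cohort 2, rule 3b. If the reference date is treatment start, the later of 01SEP2015 and 11MAR2014 is 01SEP2015 = Day −19, and the AE is lost. If it is the first on-study dose, the later of 01SEP2015 and 21SEP2015 is 21SEP2015 = Day 2, and the AE counts.

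**All entry days of 2015, with a 2014 treatment start**

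| Record | Entry days giving a date before Day 1 |
|---|---|
| Year only (rule 3a) | 365 − 1 = 364 (exception: entry on 01 January) |
| Entry month known (rule 3b), reference = treatment start | 365 − 12 = 353 (exceptions: entry on the first of a month) |
| Entry month known (rule 3b), reference = first on-study dose | 0 |

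These counts show how reliably the rule misdates a qualifying record. They do not show how often such records occur. The SAP 5.1 check against the AE end date cannot correct the result, because it can only move a start date earlier.

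**Effect per misdated event**

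- Primary percentage, planned n of 100 to 200 (SAP 8.1.2), if it is the patient's only qualifying AE: 1/100 = 1.0 point; 1/200 = 0.5 point.
- Rate for a preferred term: D/T becomes (D − 1)/T, a relative loss of 1/D. At D = 3 this is 33%; at D = 10 it is 10%. At D = 3 only 2 occurrences remain, and SAP 8.4.1 displays only terms with more than 2, so the term leaves the table.

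**Dose intensity.** Let P be pre-study time, S on-study time and C the on-study cumulative dose. The on-study value is C/S. With an on-study numerator the SAP formula gives C/(P + S), so the ratio to the on-study value is S/(P + S), whatever the dosing pattern.

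| Months before entry | Months on study | S/(P + S) |
|---|---|---|
| 3 | 36 | 36/39 = 0.92 |
| 12 | 36 | 36/48 = 0.75 |
| 24 | 36 | 36/60 = 0.60 |
| 12 | 12 | 12/24 = 0.50 |

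If the numerator instead covers all treatment, the result is a whole-treatment average. It equals the on-study value only when the mean dose was the same before and after entry. The SAP does not say which numerator is meant.

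**The case against.** The strongest reply is that the treatment start date in SAP 5.1 was intended as the first on-study dose. SAP 5.2 uses the same term to decide what was taken after study treatment began, and the branch for AEs starting before treatment has little use in Cohort 2 if treatment began before consent. On that reading rule 3 never reaches an entry-year AE and the defect disappears. It may well be the intention. But SAP 6.1.2 and 8.3 both define the term explicitly for Cohort 2 as a pre-study dose, and 6.1.2 has a separate name for the first dose after consent, which 5.1 does not use. A programmer following the SAP would produce the error.

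The second reply is rarity. Missing onset dates must be queried, AE data are updated at least monthly, SAEs are reported within 24 hours, and monitoring verifies SAE documentation. A missing month is therefore unlikely, especially for SAEs. An AE that worsened on treatment still counts, and the study is exploratory. All of this stands, and it limits the size of the effect. It does not make the rule correct.

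It is also fair that the Cohort 1 result in step 2 depends on reading the undefined reference date as treatment start, and that dose intensity is a descriptive statistic. With a whole-treatment numerator, that formula is internally consistent and only its on-study label is wrong.

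**Conclusion.** The concern holds and should be fixed. As written, rule 3a dates an unresolved, month-missing, entry-year AE before Day 1 for any Cohort 2 patient who started pasireotide in an earlier calendar year, unless the first on-study dose fell on 01 January. Rules 3b, 4a and 4c cannot be programmed unambiguously. Complete dates, and partial dates after the entry month or year, are unaffected.

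The total effect cannot be computed, because the documents give neither the cohort split nor the number of dates left partial after query. It is probably small. It is nevertheless one-directional, confined to one cohort, and acts on the rates meant to support comparison between cohorts.

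The dose-intensity point also holds. Under either numerator, the Cohort 2 figure is not what the SAP and Protocol 6.3 say will be reported. The fractions 0.50 to 0.92 apply to an on-study numerator with the durations assumed above.

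**What to change.** In SAP 5.1, replace the treatment start date and both undefined reference-date terms with the date of first dose after informed consent, already defined in SAP 6.1.2, for both cohorts. Change all of them together. Defining the reference date alone would leave rule 3a as it is, and would move an AE recorded as `MAR2015` in the example to 21SEP2015 under rule 3b.

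With the full change, the example patient's records become:

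| Recorded | Rule | Imputed |
|---|---|---|
| `2015` | 4a | 21SEP2015 (Day 2) |
| `SEP2015` | 4c | 21SEP2015 (Day 2) |
| `MAR2015` | 4b | 15MAR2015 (before entry) |
| `2014` | 2a | 01JUL2014 (before entry) |
| `2016` | 3a | 01JAN2016 (Day 104) |

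No separate lower bound for Cohort 2 is needed, and the rule for a missing year stays. Cohort 1 results do not change if its reference date was meant to be treatment start, since that is the same date. SAP 5.2 uses the same anchor for concomitant medications and should be checked at the same time.

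In SAP 8.3, define dose intensity as on-study cumulative dose divided by duration of on-study exposure.

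The cost is SAP wording and one reference variable in the AE and exposure programs. No new data are needed.
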